## 1.1 Protocol Amendment: Summary of Changes

### Previous Protocol Versions

Protocol	Date
Original	05 January 2017
Amendment 1	13 March 2017
Amendment 2	05 July 2017

The purpose of this amendment is to implement the following changes:

- Section 1.0, Title Page: to change the Emergency Contact, Therapeutic Area Medical Director's fax number.  
*Rationale:* *New fax number.*
- Section 5.2.1, Inclusion Criteria: removal of the following redundancy: "Females of non-childbearing potential (either postmenopausal or permanently surgically sterile as defined above) at Screening do not require pregnancy testing at Study Day 1."  
*Rationale:* *Editorial change.*
- Section 5.2.3.3, Prohibited Therapy: moving the time point from which phototherapy (e.g., UVA, UVB, any other UV-therapy or balneotherapy) not-associated with systemic UV-sensitizing agents, topical treatment for psoriasis or any other skin condition (e.g., corticosteroids,c vitamin D analogues, vitamin A analogues, pimecrolimus, retinoids, salicylvaseline, salicylic acid, lactic acid, tacrolimus, tar, urea, and anthralin,  $\alpha$ -hydroxy acid, fruit acids) are prohibited from 14 days prior to Screening to 14 days prior to Baseline.  
*Rationale:* *The half-life of those therapies is short and no interaction with study medication is to be expected if they are discontinued 14 weeks before 1st dose of study medication, i.e., 14 days before Baseline (Day 1, Week 0).*
- Section 5.3.1.1, Study Procedures, and Appendix C, Study Activities: FUMADERM® INITIAL and FUMADERM® Subject Diary: Clarification that the subject diary will be dispensed to the subject at every visit, starting at the Week 0/Baseline Visit rather than at the Screening Visit, and that the

subject will be trained on how to complete the diary at the Week 0/Baseline Visit.

***Rationale:*** *Clarification.*

- Section [5.4.1.1](#), Discontinuation of Subjects on FUMADERM®: Point 8: Restriction of the discontinuation of the subjects on FUMADERM® for rash/flush to those with severe rash/flush.

***Rationale:*** *In clinical practice only severe persistent rash/flush leads to discontinuation of the patients from FUMADERM®.*

*The FUMADERM® label language does not request discontinuation of FUMADERM® treatment for all adverse events of rash/flush, but says: "... severe forms (of rash/flush) may lead to (FUMADERM®) treatment discontinuation."*

- Section [5.5.1](#), Treatments Administered: the sentence "Additional dosing instructions will be provided separately from this protocol" has been removed.

***Rationale:*** *Risankizumab will be administered by site personnel only, therefore no additional instructions on how to administer an SC injection is required.*

- [Appendix J](#), NAPPA-CLIN®: Extension of the prohibition of artificial nail and/or nail polish to all subjects instead of subjects with nail psoriasis only.

***Rationale:*** *Consistency within the protocol. The analysis of the efficacy on nail psoriasis is planned on all subjects regardless of a concomitant nail psoriasis.*

An itemized list of all changes made to this protocol under this amendment can be found in [Appendix K](#).

## 1.2 Synopsis

AbbVie Inc.	Protocol Number: M16-178
Name of Study Drug: Risankizumab	Phase of Development: 3
Name of Active Ingredient: Risankizumab	Date of Protocol Synopsis: 28 November 2017
Protocol Title: A Randomized, Controlled, Multicenter, Open Label Study with Blinded Assessment of the Efficacy of the Humanized Anti-IL-23p19 Risankizumab Compared to FUMADERM® in Subjects with Moderate to Severe Plaque Psoriasis who are Naïve to and Candidates for Systemic Therapy	
Objective: The objective of this study is to compare the efficacy and safety of subcutaneous (SC) risankizumab and oral FUMADERM® provided as study medication in subjects with moderate to severe plaque psoriasis who are naïve to and candidates for systemic therapy.	
Investigator: Investigator information on file at AbbVie.	
Study Site: Approximately 25 sites in Europe	
Study Population: Adults with moderate to severe plaque psoriasis [Psoriasis Area and Severity Index (PASI > 10), affected body surface area (BSA) > 10% and Dermatology Life Quality Index (DLQI) > 10] who are naïve to and candidates for systemic therapy.	
Number of Subjects to be Enrolled: Approximately 110 [2 × 55]	
Methodology: This study is a randomized, controlled, multicenter, open-label study with blinded assessment of efficacy to demonstrate the efficacy and safety of SC risankizumab in adult subjects with moderate to severe plaque psoriasis who are naïve to and candidates for systemic therapy compared with oral FUMADERM® provided as study medication. This study will be conducted in approximately 110 subjects. Subjects will be randomized in a 1:1 ratio (stratified by prior phototherapy, with a maximum of 20% of subjects with prior phototherapy) to one of two arms of either risankizumab or oral FUMADERM® provided as study medication. The following are the dosing arms: 

• Risankizumab 150 mg SC at Week 0/Day 1, Week 4 and Week 16 or,

• Oral FUMADERM® provided as study medication daily starting at Week 0/Day 1 and until Week 24 (last intake in the morning on the day of Week 24 visit): FUMADERM® INITIAL provided as study medication starting at Week 0/Day 1 until Week 2 and FUMADERM® provided as study medication starting at Week 3, both at starting dose of 1 tablet per day, followed by an increase in the daily dose of 1 tablet per week, with the intention of achieving PASI 90. The maximum daily dose of FUMADERM® provided as study medication may not exceed 6 tablets per day. After the targeted efficacy on the psoriasis cutaneous lesions has been reached, an attempt should be made to reduce the dose of FUMADERM® provided as study medication to the individual maintenance dose.

 Efficacy outcomes will be measured at each visit until Week 24 and safety data will be collected throughout the study.	

**Methodology (Continued):**

At the Week 24 visit, subjects who completed the study will be offered the opportunity to participate in a separate extension study. For subjects that do not elect to enroll into the extension study, a follow-up phone call will be performed at Week 31.

**Diagnosis and Main Criteria for Inclusion/Exclusion:****Main Inclusion:**

1. Male or female subject  $\geq$  18 and  $<$  80 years of age at the time of screening.
2. Have a diagnosis of chronic plaque psoriasis for at least 6 months before the first administration of study drug. Duration since diagnosis may be reported by the patient.
3. Subject has stable moderate to severe plaque psoriasis with or without psoriatic arthritis at Baseline
  - Has an involved BSA  $>$  10% and
  - Has a PASI score  $>$  10 and
  - Has a DLQI  $>$  10.
4. Must be naïve to and candidate for systemic therapy, as assessed by the investigator.
5. Subject has an inadequate response, intolerance or contraindication to topical psoriasis treatment as documented in the patient's medical history or reported by the patient or determined by the investigator at screening.

**Main Exclusion:**

1. Subjects with
  - Non-plaque forms of psoriasis (including guttate, erythrodermic, or pustular)
  - Drug-induced psoriasis (including an exacerbation of psoriasis from beta blockers, calcium channel blockers, or lithium)
  - Active ongoing inflammatory diseases other than psoriasis that might confound study evaluations according to investigator's judgment
2. Subject has previously received systemic therapy for psoriasis, whether biologic or non-biologic, or photochemotherapy (e.g., PUVA therapy, any UV-therapy or balneotherapy associated with UV-sensitizing agent).
3. Active systemic infection during the last 2 weeks (exception: common cold) prior to screening.
4. Any documented active or suspected malignancy or history of malignancy within 5 years prior to screening, except appropriately treated basal or squamous cell carcinoma of the skin or in situ carcinoma of uterine cervix.
5. Subject has any condition or contraindication to FUMADERM® that would preclude the patient's participation in the present study, including, but not limited to:
  - A known hypersensitivity to fumaric acid derivatives or other components of FUMADERM® Initial or FUMADERM®,
  - Any parameter of the complete blood count (CBC), at Screening Visit, outside of normal range according to the central laboratory
  - Severe liver disease (ALT or AST  $>$  2  $\times$  ULN according to central laboratory normal range, or total bilirubin  $>$  1.5  $\times$  ULN according to central laboratory normal range at Screening visit),
  - Severe kidney disease (serum creatinine above normal value according to central laboratory normal range at Screening visit),

**Diagnosis and Main Criteria for Inclusion/Exclusion (Continued):****Main Exclusion (Continued):**

- Severe gastro-intestinal disease, such as a known active gastro-duodenal ulcer,
- Inability to understand the complexity of FUMADERM® dosing regimen,
- Any other exclusionary condition provided in Fumaderm® local label,
- Any of the following risk factors for renal toxicity:
  - peripheral vascular disease
  - diabetes mellitus with microalbuminuria (UACR > 30 mg/g), at Screening Visit,
  - systolic blood pressure measurement of > 140 mmHg or a diastolic blood pressure measurement of > 90 mmHg at the Screening visit, unless there is confirmation from an internist or a cardiologist that no renal or cardiovascular risk is associated with the elevated blood pressure.
  - history of congestive heart failure (NYHA Class III or IV\*)

**Investigational Product:** Risankizumab**Doses:** 150 mg at Weeks 0 and 4, and 16.**Mode of Administration:** Subcutaneous Injection (SC) (pre-filled syringe)**Investigational Product:** FUMADERM® INITIAL and FUMADERM® provided as study medication**Doses:** QD to TID**Mode of Administration:** Oral**Duration of Treatment:** The treatment duration will be 16 weeks for risankizumab and 24 weeks for FUMADERM®.**Criteria for Evaluation:****Efficacy:**

The primary efficacy endpoint is the proportion of subjects with a  $\geq 90\%$  improvement in Psoriasis Area and Severity Index (PASI90) at Week 24.

Secondary efficacy variables are:

PASI, Body Surface Area (BSA), static Physician Global Assessment (sPGA), Palmoplantar psoriasis Severity Index (PPASI), Psoriasis Scalp Severity Index (PSSI), Nail Assessment in Psoriasis and Psoriatic Arthritis (NAPPA-CLIN), Total Score Psoriasis Symptom Scale (PSS), Dermatology Life Quality Index (DLQI), Short Form 36 (SF-36) Physical Component Summary (PCS) and Mental Component Summary (MCS) Scores, Patient Benefit Index (PBI), Hospital Anxiety and Depression Scale (HADS) Patient Global Assessment (PtGA), European quality of life – 5 dimensions 5 Level (EQ-5D-5L)

**Pharmacokinetics and Immunogenicity:**

Blood samples will be collected for measurement of risankizumab concentration and anti-drug antibody (ADA) between Day 1/Week 0 and Week 24/early termination (ET) visits.

**Safety:**

Safety and tolerability evaluations include adverse event monitoring, physical examinations, vital sign measurements, and clinical laboratory testing (hematology, chemistry, and urinalysis). Toxicity management guidelines are provided within the study protocol.

**Statistical Methods:****Efficacy:**

The efficacy analysis will be performed in the Intent to Treat (ITT) set which includes all subjects who are randomized.

The primary efficacy endpoint (PASI90 at Week 24) will be analyzed using a two-sided Cochran-Mantel Haenszel test stratified by prior phototherapy at level of significance 5%. Missing data will be imputed using non-responder imputation, i.e., a subject with missing PASI90 at Week 24 will be considered a non-responder in the primary analysis.

For categorical secondary endpoints, the same statistical test as for the primary endpoint will be used, missing data will be imputed using non-responder imputation. For continuous secondary endpoints, two-sided two-way ANOVA will be used with treatment and prior phototherapy as factors and missing data will be imputed using last observation carried forward (LOCF).

Secondary endpoints will not be used for confirmatory interpretation, thus no adjustment for multiplicity will be done.

**Pharmacokinetics (PK) and Immunogenicity:**

Risankizumab serum concentrations will be determined. Descriptive statistics will be calculated for each sampling time (study visit). The number and percentage of subjects with ADA will be calculated.

Additional analyses combining pharmacokinetic and ADA data from this study and other studies may be conducted if appropriate.

**Safety:**

The safety analysis will be performed in the safety set which includes all subjects who received at least one dose of study drug.

Treatment-emergent adverse events will be tabulated by system organ class and preferred term, whereby the most current implemented MedDRA dictionary will be used. Also, summaries by severity and relationship to study drug will be done. Certain adverse events, like serious or severe, leading to discontinuation, will be listed and described in detail. Adverse events of interest for treatment with biologics will be defined in the statistical analysis plan and analyzed separately.

Adverse events will be summarized by frequency and percentage and presented by treatment group, statistical comparisons will be performed using Fisher's exact test.

Other safety variables like laboratory data and vital signs will also be described by descriptive statistics for each treatment group. Treatment comparisons will be performed by one way ANOVA. In addition, shift tables and listings will be provided for abnormal values, whereby the normal range of the analyzing laboratory will be used.

\* Criteria Committee, New York Heart Association, Inc. Diseases of the heart and blood vessels. Nomenclature and criteria for diagnosis, 6th edition Boston, Little, Brown and Co. 1964, p 114.

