**Figure 1. PASI 90 Over Time (Observed) – Full Analysis Set**

The 12 week data indicate a 37% greater improvement for risankizumab (90 mg and 180 mg, pooled data) compared to ustekinumab in the proportion of subjects achieving PASI 90.

The current study compares the safety and efficacy of risankizumab versus Fumaderm® provided as study medication in subjects with moderate to severe psoriasis.

For a more detailed description of the drug profile, refer to the latest version of the investigator's brochure (IB).

Fumaric acid esters was approved in Germany as systemic therapy for the treatment of psoriasis in 1995. The commercial product, Fumaderm® contains a mixture of dimethyl fumarate (DMF) and three salts of ethyl hydrogen fumarate. DMF is considered to be the actual active ingredient.

Most of the reports on the clinical effects of Fumaderm® on psoriasis are from open label studies that consistently showed that a significant improvement in the condition of the skin is reached over a period of about 3 months of treatment.

Preliminary results of a recent adequate and well controlled clinical study including a Fumaderm® arm indicate that PASI 75 and PGA 0 or 1 responses were achieved at Week 16 in 40.3% and 37.4% of the subjects treated with Fumaderm®, whereas 22.3% of the subjects achieved PASI 90 at Week 16.

Serious adverse events were reported in 2.8% of the subjects and discontinuation due to adverse events occurred in 24% of the subjects receiving FUMADERM®. The most frequently reported treatment-emergent adverse events (TEAEs) were gastrointestinal disorders, including diarrhea (39.9%), upper abdominal pain (22.6%), abdominal pain (15.9%) and nausea (8.5%). Flushing was also commonly reported (16.3%) as well as pruritus (9.9%). Lymphopenia was observed in 10.6% of the subjects and was considered severe in two subjects (0.07%). Erythema, headache and nasopharyngitis were also reported (8.1% each). Proteinuria was reported in 2.1% of the subjects.

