Fumaderm® is a widely prescribed systemic therapy for moderate to severe psoriasis, although registered for this indication in Germany only, a high proportion of patients treated with FUMADERM® experience a significant improvement in their psoriatic skin disease over a period of about 3 months of treatment.

The safety profile of FUMADERM® is well characterized. Gastrointestinal complaints (in up to 60% of subjects especially in the initial weeks of therapy) and flush are the most common side effects of fumaric acid esters. Gastrointestinal tract symptoms include diarrhea, increased frequency of stools, nausea, and abdominal cramps. The symptoms of flush are highly variable and range from a brief feeling of warmth to reddening of the face

lasting for several hours. Leukocytopenia, lymphocytopenia, and eosinophilia are common side effects of fumaric acid esters. The other adverse events reported in association with FUMADERM® remain uncommon to very rare: acute lymphocytic leukemia, increase in liver function tests, Fanconi syndrome, opportunistic infection increases including isolated cases of progressive multifocal encephalopathy.

There is no known association of FUMADERM® with malignancy.

There are no studies on the use of fumaric acid esters during pregnancy or in nursing women. Toxicology studies have shown that fumaric acid esters have neither teratogenic nor mutagenic potential.

The well codified dosing schedule for FUMADERM®, based on individual efficacy and safety response and the long experience in clinical practice since its commercialization guarantees an acceptable risk-benefit balance. Pregnancy and breastfeeding as well as severe liver, kidney and gastrointestinal diseases are contraindication to Fumaderm®.

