## **4.0 Study Objective**

The objective of this study is to compare the efficacy and safety of SC risankizumab and oral FUMADERM® provided as study medication in subjects with moderate to severe plaque psoriasis who are naïve to and candidates for systemic therapy.

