## **8.2 Determination of Sample Size**

Using a two-sided Chi squared test at level of significance 5%, the sample size of 110 (2 × 55) subjects will provide 94% power assuming response rates of the primary endpoint (PASI90 at Week 24) of 70% for risankizumab and 35% for FUMADERM®.

These assumptions are in line with what has been observed in recent studies for Risankizumab (63/83 (75.9%) at Week 24) and FUMADERM® 61/273 (22.3%) of the subjects achieved PASI 90 at Week 16 in the FUMADERM® arm in the BRIDGE trial.

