**Areas of Safety Interest**

Areas of Safety Interest groupings are listed in [Table 6](#). These events are of interest due to a higher rate in the moderate to severe psoriasis population, or of interest for all immunoglobulin products or products in general.

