**Table 6. Areas of Safety Interest**

ASI Grouping	Categories (ASI)	Search Criteria	Terms to Display	Include in AE Overview (Y/N)
Adjudicated CV Events	MACE	Adjudicated events	
Display underlined terms defined by the following adjudicated terms:
 
 
• CV Death which includes CETERM values: Fatal CV, Fatal PE, Fatal Non-Cardiac/Non-Neuro Arterial Thrombosis/Thromboembolism, Undetermined Death, Not assessable death (cardiac/neuro/thrombotic), Fatal Stroke
 
• Myocardial infarction
 
• Stroke
 
	Y
	Extended MACE	Adjudicated events	
Display underlined terms from MACE and underlined terms below:
 
 
• Hospitalization for Unstable Angina
 
• Coronary Revascularization Procedures
 
	N
Serious infections, TB, fungal and opportunistic infections (including herpes zoster)	Serious infections	SOC Infections and Infestations, serious events only	PTs	Y
	TB	Tuberculosis (including Investigations) CMQ (code 80000033)	PTs	Y
	Opportunistic infections	Opportunistic infections CMQ (code 80000073)	PTs	N

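### The separately analysed safety topics leave out flush, leukopenia/lymphopenia and renal events, so these named FUMADERM harms get no overview line and no exposure-adjusted rate in a comparative safety trial

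*Protocol*

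**What the plan says.** Protocol section 4.0 sets a comparative aim: "The objective of this study is to compare the efficacy and safety of SC risankizumab and oral FUMADERM". For events to be analysed separately, the safety text in synopsis 1.2, repeated in 8.1.5, says: "Adverse events of interest for treatment with biologics will be defined in the statistical analysis plan and analyzed separately".

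SAP 11.2.1 explains the choice of topics by their higher rate in moderate to severe psoriasis, "or of interest for all immunoglobulin products or products in general". Table 6 then lists adjudicated cardiovascular events; serious, tuberculous, opportunistic and fungal infections and herpes zoster; malignancies; hypersensitivity; and hepatic events. Some searches deliberately cross organ classes: the tuberculosis row is "Tuberculosis (including Investigations) CMQ (code 80000033", and the hepatic row includes liver-related investigations.

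The protocol describes the comparator's harms elsewhere. Section 3.2 calls gastrointestinal complaints and flush the most common ones and adds: "Leukocytopenia, lymphocytopenia, and eosinophilia are common side effects of fumaric acid esters". It also lists Fanconi syndrome. Section 3.0 gives rates from a controlled trial with a FUMADERM arm: diarrhea 39.9%, flushing 16.3%, erythema 8.1%, proteinuria 2.1%, and "Lymphopenia was observed in 10.6% of the subjects". Several of these toxicities are triggers for discontinuation (5.4.1.1) or dose reduction (5.5.1).

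Under SAP 11.2.1, rates per 100 patient-years are planned for any treatment-emergent event, serious events and the areas of safety interest. All other events are tabulated by organ class and preferred term. SAP 11.1 compares the arms by Fisher's exact test and shows only p-values of 0.100 or less.

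**The concern.** A topic listed in Table 6 gets its own table and listing and an exposure-adjusted rate and, where the table says so, a line in the overview. A topic that is absent gets organ-class and preferred-term rows only. Flush, low white cell counts and renal events are among the harms a reader would most want compared with risankizumab, and they fall in the second class.

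A second issue is coding. Protocol 6.1 has the investigator record a diagnosis if known, otherwise a sign or symptom. A laboratory abnormality becomes an adverse event only if it leads to discontinuation or treatment, or if the investigator judges it to be one. The same toxicity could therefore be entered under different terms in different subjects. The SAP allows for this in its own topics but has no pooled count for the comparator's. At stake are the prominence and precision of the safety comparison, not the primary result.

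**Working it through.** **1. The plan's own figure.** Protocol 8.2 states: "Using a two-sided Chi squared test at level of significance 5%, the sample size of 110 (2 × 55) subjects will provide 94% power". The PASI 90 rates behind it are 70% and 35%. At 55 per arm, the uncorrected chi-squared test gives 96.6% by normal approximation and 96.2% by exact enumeration. The continuity-corrected version gives 94.8% and Fisher's test 94.2%. The stated 94% is attainable and slightly conservative. It concerns PASI 90 only; no adverse event comparison was sized.

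**2. What each comparator harm receives.**

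| Harm named for FUMADERM | Table 6 group | Other coverage |
|---|---|---|
| Hepatic events, opportunistic infections | Yes, but overview flag is N | Organ class/term; liver tests for hepatic events |
| Gastrointestinal | No | Organ-class row pools them |
| Leukopenia/lymphopenia | No | Organ class/term; blood counts |
| Renal/proteinuria | No | Organ class/term; creatinine, UACR |
| Flush/erythema | No | Organ class/term only |

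**3. Power of the planned test.** Inputs: n = 55 per arm (Protocol 8.2); FUMADERM rates from Protocol 3.0; risankizumab rates of 1%, 2% and 5%, which are assumptions because the documents give none for these terms. Formula: power = Σₐ Σ_b Bin(a; 55, p_F) × Bin(b; 55, p_R), summed over pairs whose two-sided Fisher p, rounded to three decimals, is at most 0.05.

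| Event, FUMADERM rate | Expected count (55 × rate) | Risankizumab 1% | 2% | 5% |
|---|---|---|---|---|
| Diarrhea, 39.9% | 21.9 | 100% | 100% | 99.6% |
| Flushing, 16.3% | 9.0 | 78% | 66% | 36% |
| Flush or erythema, no overlap, 16.3% + 8.1% = 24.4% | 13.4 | 98% | 94% | 78% |
| Lymphopenia, 10.6% | 5.8 | 39% | 27% | 9% |
| Proteinuria, 2.1% | 1.2 | 0.1% | 0.1% | 2% |

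If flush and erythema overlap fully, the grouped rate stays at 16.3% and the flushing row applies. For the gastrointestinal organ class at 60% (the upper figure in Protocol 3.2), power is 99% even with risankizumab at 20%. At 39.9%, the least it can be if diarrhea is that frequent, power is 95% against 10% and 56% against 20%.

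**4. What splitting could do.** Suppose, for illustration only, that one toxicity divides evenly over two terms and risankizumab totals 2%. Lymphopenia then falls from 27% grouped to 4% per term, and flushing from 66% to 19%. In counts, 6 against 0 gives p = 0.027. The same events as two terms of 3 against 0 give p = 0.243 each, above the display limit, though the counts would still be printed.

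**The case against.** The strongest reply is that the gap is small and largely covered.

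- A reader might infer that the topics serve the biologic alone. The documents do not support that. Hepatic events and opportunistic infections are FUMADERM risks in Protocol 3.2 and are grouped, and the SAP's rationale extends to products in general.
- A reader might infer that real differences go unreported. They do not. Counts and percentages are tabulated by organ class, term, severity and relationship, and discontinuations due to adverse events have their own table and listing. The display rule hides only p-values.
- A reader might infer that the comparator's harms as a whole are weakly compared. That fails for gastrointestinal events, which are pooled by their organ-class row and well powered.
- Blood counts and creatinine are measured at every treatment visit. SAP 11.3.2 summarises change from baseline, shifts against the normal range and grade 3 or worse values, however events were coded.
- The even split is not in the documents, which do not show the dictionary structure. If 10.6% is already a single-term rate, per-term power is the unsplit figure.
- Under-emphasis of comparator harms does not flatter risankizumab.

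All of this stands, and it limits the point to a reporting asymmetry. It does not remove it. The laboratory cover is incomplete: SAP Table 7 omits eosinophils and dipstick urine protein, which the protocol collects, and SAP 11.3.2 lists only descriptive summaries where Protocol 8.1.5 plans ANOVA comparisons. Flush has no laboratory counterpart at all.

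**Conclusion.** The point holds as a moderate reporting gap. The separately analysed topics were chosen mainly from the biologic and psoriasis viewpoint. Flush/erythema, leukopenia/lymphopenia and renal/proteinuria events, all named comparator harms, lack an overview line, an area-of-interest table and a rate of their own. Gastrointestinal events lack only the overview line and the rate.

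The benefit of grouping differs by event. It is certain for presentation. For power it depends on one toxicity really being coded under several terms, which is an assumption, as are the risankizumab rates. Lymphopenia has low power at 10.6% (9% to 39%). Flushing is moderate (36% to 78%) and could rise to 78% to 98% if erythema were added without overlap. Proteinuria at 2.1%, about one subject in 55, cannot be rescued by grouping. The primary endpoint and the sample size are unaffected.

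**What to change.** Before database lock, add to SAP Table 6 prespecified groups for flush (with erythema), leukopenia/lymphopenia and renal/proteinuria events. Apply them to both arms, fix the preferred-term lists in advance, search across organ classes including Investigations, and set the overview flag to Y. The existing area-of-interest tables and rates per 100 patient-years then cover them without new methods. A gastrointestinal row for the overview and rate tables is optional.

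Reword the sentence in synopsis 1.2 and Protocol 8.1.5 so that it refers to adverse events of interest for either study treatment.

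The cost is a term list from medical coding and three or four more rows in planned tables. Because the trial is open-label, fixing the groups beforehand also avoids groupings chosen after the data are seen.
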